## **Study Phases**

### Recruitment and Selection of SCT cases (Phenotype phase)

We plan to recruit 120 adults (20% screen fail rate), to evaluate at the screening visit approximately 100 adults with ADHD at two sites (NYU and Mount Sinai) to identify 50 SCT+ and 50 SCT-. These patients will be evaluated with clinical measures of SCT (Barkley SCT Scale), ADHD (ADHD-RS with prompts), executive function (BRIEF-A), assessment of other psychiatric disorders (M.I.N.I.), global impairment (CGI), functional impairment (Barkley Functional Impairment Scale (BFIS)), suicidality (C-SSRS), and neuropsychological function (neuropsychological battery). Only patients in the SCT+ cohort will enter the treatment phase of the protocol.

### LDX Treatment Phase

We are proposing a 2-site (NYU and Mount Sinai) study of LDX in 50 adults with ADHD + SCT. The study will be a double-blind, 10-week, cross-over treatment trial of LDX (4 weeks; 30 – 70 mg/day) vs. placebo (4 weeks) with an intervening single-blind placebo washout period (2 weeks). During the LDX treatment epoch, LDX treatment will be initiated at a dose of 30mg/day at Visit 2 and can be titrated up (in the judgment of the investigator) in increments of 20mg, based upon clinical response and tolerability, to 50mg/day at Visit 1 and 70mg/day at Visit 3. Subjects receiving daily doses of 50mg or 70mg of LDX will be allowed to down titrate one dosage step of 20mg during Visits 3-5 if (in the judgment of the investigator) they are having issues in tolerability. The highest effective dose of LDX will then be maintained until Visit 6. Patients will be seen weekly throughout the trial except during placebo washout. The same schedule will occur during Phase 2 of the study.

CONFIDENTIAL

During the Phase 2 LDX treatment epoch, LDX treatment will be initiated at a dose of 30mg/day at Visit 7 and can be titrated up (in the judgment of the investigator) in increments of 20mg, based upon clinical response and tolerability, to 50mg/day at Visit 1 and 70mg/day at Visit 8. The titration procedure will follow that of phase 1.

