### **5.2 Treatment Regimen**

Medication will not be dispensed until week 1 of the study. Then for four weeks the dose of LDX or Placebo will be dispensed starting at 30mg up to 70 mg per day with an intervening single-blind placebo washout period (2 weeks).

Block One: During the LDX/epoch, LDX/Placebo treatment will be initiated at a dose of 30mg/day at Visit 2 and can be titrated up (in the judgment of the investigator) in

CONFIDENTIAL

increments of 20mg, based upon clinical response and tolerability, to 50mg/day at Visit 3 and 70mg/day at Visit 4.

Subjects receiving daily doses of 50mg or 70mg of LDX/Placebo will be allowed to down titrate one dosage step of 20mg during Visits 3-5 if (in the judgment of the investigator) they are having issues in tolerability. The highest effective dose of LDX will then be maintained until Visit 6.

Placebo Washout: At this time the patient are in the washout placebo phase for two weeks.

Block Two: At the end of the Placebo Washout Phase, Visit 7 (week 6), participants will be initiated at a dose of 30mg/day and can be titrated up starting at Visit 8 (in the judgment of the investigator) in increments of 20mg, based upon clinical response and tolerability.

Subjects receiving daily doses of 50mg or 70mg of LDX/Placebo will be allowed to down titrate one dosage step of 20mg during Visits 8-10 if (in the judgment of the investigator) they are having issues in tolerability. The highest effective dose of LDX will then be maintained until Visit 11

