### **7.1 Sample Size Determination**

Phase I: Recruitment and Selection of SCT cases (Phenotype phase)

We plan to recruit 120 adults (20% screen fail rate) to evaluate at the screening visit; approximately 100 adults with ADHD at two sites (NYU and Mount Sinai) to identify 50 SCT+ and 50 SCT-. These patients will be evaluated with clinical measures of SCT (Barkley SCT Scale), ADHD (ADHD-RS with prompts), executive function (BRIEF- A), assessment of other psychiatric disorders (M.I.N.I) global impairment (CGI), functional impairment (FIRS- QS), suicidality (C-SSRS), and neuropsychological function (neuropsychological battery). Only patients in the SCT+ cohort will enter the treatment phase of the protocol.

Phase II: Treatment Phase

We are proposing a 2-site (NYU and Mount Sinai) study of LDX in 50 adults with

CONFIDENTIAL

ADHD + SCT. The study will be a double-blind, 10-week, cross-over treatment trial of LDX (4 weeks; 30 – 70 mg/day) vs. placebo (4 weeks) with an intervening single-blind placebo washout period (2 weeks). During the LDX treatment epoch, LDX treatment will be initiated at a dose of 30mg/day at Visit 2 and can be titrated up (in the judgment of the investigator) in increments of 20mg, based upon clinical response and tolerability, to 50mg/day at Visit 3 and 70mg/day at Visit 4. Subjects receiving daily doses of 50mg or 70mg of LDX will be allowed to down titrate one dosage step of 20mg during Visits 2-4 if (in the judgment of the investigator) they are having issues in tolerability. The highest effective dose of LDX will then be maintained until Visit 4. Patients will be seen weekly throughout the trial.

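### The titration, down-titration and dose-hold visits contradict each other across Sections 3.1, 5.2 and 7.1, and Section 3.1 cannot be followed as written

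*Combined protocol and SAP*

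**What the plan says.** **Section 3.1, LDX Treatment Phase.** In block 1, "LDX treatment will be initiated at a dose of 30mg/day at Visit 2". The dose may then rise, at the investigator's judgment, "in increments of 20mg, based upon clinical response and tolerability", with the steps placed "to 50mg/day at Visit 1 and 70mg/day at Visit 3". Subjects on 50 or 70 mg may "down titrate one dosage step of 20mg during Visits 3-5" for tolerability, and the dose is then held to Visit 6. For block 2 the start is 30 mg at Visit 7, with the steps placed "to 50mg/day at Visit 1 and 70mg/day at Visit 8". The section says that block 2 follows the block 1 procedure.

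**Section 5.2, Treatment Regimen.** Block 1 starts at Visit 2 and rises "to 50mg/day at Visit 3 and 70mg/day at Visit 4". Down-titration is at Visits 3-5 and the hold runs to Visit 6. Block 2 starts at Visit 7 and may be titrated from Visit 8 in 20 mg steps, but no visit is named for 70 mg. Block 2 down-titration is at Visits 8-10 and the hold runs to Visit 11.

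**Section 7.1, Sample Size Determination.** The block 1 steps are at Visits 3 and 4, as in 5.2. Subjects on 50 or 70 mg may "down titrate one dosage step of 20mg during Visits 2-4", and then: "The highest effective dose of LDX will then be maintained until Visit 4". No block 2 visits are given.

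**The concern.** These are operative dosing instructions for a stimulant, and a site that reads one section will act differently from a site that reads another. Section 4.3 says that the two sites have their own staff and pharmacies, so nothing in the text ensures that both work from the same section.

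Three things are at stake:

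- **Safety.** Section 1.6.1 lists raised blood pressure and tachycardia among the drug's risks. How fast and when the dose may rise or fall should not be open to interpretation.
- **The primary result.** The power statement in 3.1 rests on change from baseline to week 4 on the Barkley SCT scale. The model in 7.2 reads the treatment effect from the visit-by-treatment interaction. When a subject can reach a given dose affects the trajectory under test, and the terms listed for that model do not include site.
- **Compliance.** The protocol-compliant population in 7.3 requires the drug exposure that the protocol specifies, and 8.3.1 requires deviations to be reported. Neither can be judged against schedules that conflict.

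**Working it through.** No sample-size, power or error-rate figure is involved, so the check is a comparison of the texts after converting visits to study days.

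**Step 1. Visit timing (Section 6 table and Sections 6.1 to 6.8).** Visit 1 is screening, week -3 to week 0. Visit 2 is Day 0. Visits 3, 4 and 5 are Days 7, 14 and 21. Visit 6 is Day 28 (end of treatment 1). Visit 7 is Day 42. Visits 8, 9 and 10 are Days 49, 56 and 63. Visit 11 is Day 70. On-treatment visits have a ±2 day window. Under Section 6.2, drug is first handed out at Visit 2.

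**Step 2. The sections side by side.**

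| Element | Section 3.1 | Section 5.2 | Section 7.1 |
|---|---|---|---|
| Block 1, 30 mg | Visit 2 (Day 0) | Visit 2 (Day 0) | Visit 2 (Day 0) |
| Block 1, 50 mg | Visit 1 (screening) | Visit 3 (Day 7) | Visit 3 (Day 7) |
| Block 1, 70 mg | Visit 3 (Day 7) | Visit 4 (Day 14) | Visit 4 (Day 14) |
| Block 1, down-titration | Visits 3-5 | Visits 3-5 | Visits 2-4 |
| Block 1, hold until | Visit 6 (Day 28) | Visit 6 (Day 28) | Visit 4 (Day 14) |
| Block 2, 30 mg | Visit 7 (Day 42) | Visit 7 (Day 42) | not given |
| Block 2, 50 mg | Visit 1 (screening) | titration from Visit 8 (Day 49) | not given |
| Block 2, 70 mg | Visit 8 (Day 49) | no visit named | not given |

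**Step 3. Section 3.1 on its own terms.** The 50 mg step falls at a visit before the 30 mg start in both blocks, so it cannot be carried out. The 70 mg step falls 7 - 0 = 7 days after 30 mg in block 1 and 49 - 42 = 7 days after it in block 2. The only dose change that can be placed in that week is 70 - 30 = 40 mg, against the 20 mg increment in the same sentence.

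**Step 4. Section 7.1 on its own terms.** Its down-titration window opens at Visit 2, when subjects are only starting 30 mg and nobody is on 50 or 70 mg. Its hold ends on Day 14, the day on which it first permits 70 mg. From Day 14 to Day 28 (28 - 14 = 14 days) it gives no dose rule.

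**Step 5. Longest nominal time at 70 mg before the end-of-block rating.**

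- Block 1 under 3.1: 28 - 7 = 21 days.
- Block 1 under the 5.2 and 7.1 visits: 28 - 14 = 14 days.
- Block 2 under 3.1: 70 - 49 = 21 days.
- Block 2 under 5.2, assuming one 20 mg step per visit so that 70 mg falls at Visit 9: 70 - 56 = 14 days.

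The nominal difference is 21 - 14 = 7 days. Each interval runs between two visits with ±2 day windows, so it can move by up to 4 days either way: 17 to 25 days and 10 to 18 days.

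**The case against.** The strongest reply is that this is a drafting slip with an obvious majority reading. On each block 1 element two of the three sections agree: 5.2 and 7.1 on the up-titration visits, 3.1 and 5.2 on down-titration and the hold. Section 5.2 carries the title for treatment, and 7.1 is a sample-size section from which a site may never dose. The agreement is real, and it means that this is not a three-way conflict on every element. It does not settle the matter. The protocol does not say that 5.2 governs, and for block 2 the only visit named for 70 mg anywhere is the one in 3.1.

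A reader might also infer four stronger things that the documents do not support:

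- **That 3.1 authorises a 40 mg step.** It does not. The same sentence limits steps to 20 mg and names 50 mg in between. The jump appears only if the impossible Visit 1 step is discarded and the increment limit is set aside. Section 3.1 is self-contradictory; it is not permissive.
- **That 21 and 14 days are times at a maintained dose.** They are upper limits for time at 70 mg. Titration is optional. Under 5.2, a subject kept at 30 mg has a stable dose for 28 days, one at 50 mg from Visit 3 for 28 - 7 = 21 days, and one stepped down at Visit 5 for 28 - 21 = 7 days.
- **That 7.1 leaves no maintenance time at all.** That is so only for subjects first reaching 70 mg at Visit 4. A subject kept at 30 mg has 14 days before Visit 4, and one raised to 50 mg at Visit 3 has 14 - 7 = 7 days.
- **That the two blocks have different schedules.** No section says so. Section 3.1 states that they match, and its 70 mg visit falls one week after the start in both. In 5.2, titration opens one week after the start in both.

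**Conclusion.** The contradiction is real and lies in current operative text. Section 3.1 cannot be followed in either block. Section 7.1 opens down-titration at a visit where it cannot apply and leaves the second half of block 1 without a dose rule. Sections 5.2 and 7.1 between them do not complete the block 2 schedule.

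The size is a nominal 7-day difference in the earliest visit for 70 mg, and so in the longest possible exposure at 70 mg before the primary rating (21 against 14 days). This rests on the visit calendar in Section 6 and, for block 2 under 5.2, on an assumed one step per visit. It is a bound and not an expected difference, because the documents do not say how many subjects would be titrated to 70 mg or which section either site uses. Different dosing at the two sites is possible under the text; the documents do not show that it occurs.

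**What to change.** The sponsor and investigator must reconcile Sections 3.1, 5.2 and 7.1 into one schedule for titration, down-titration and dose hold. It should cover both blocks, use the visit numbering of Section 6 and leave no interval without a rule. State it in one section and replace the other two descriptions with a cross-reference. Which of the conflicting visits is right is a clinical decision for them, and no view is given here.

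The cost is a wording amendment, submitted to the IRB as Section 11 already requires. It adds no procedures or visits and leaves the sample size unchanged.

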### **3.2 Primary Study Endpoints**

The primary study endpoint is to examine the efficacy of lisdexamfetamine dimesylate (LDX) versus placebo on symptoms of sluggish cognitive tempo (SCT) in adults with ADHD and SCT.

### **3.3 Secondary Study Endpoints**

The secondary study endpoints are to define the SCT phenotype and determine similarities and differences between adults with ADHD with and without SCT on SCT symptoms, executive function symptoms, nature and severity of ADHD symptoms, and neuropsychological profile

## **4 Subject Selection and Withdrawal**

### **4.1 Inclusion Criteria**

- 1) Male or female between the ages of 18-60 of all races and ethnicity.
- 2) Meets DSM-IV-TR criteria for a primary diagnosis of inattentive or combined type ADHD as diagnosed via the Adult ADHD Clinician Diagnostic Scale version 1.2 (ACDS v1.2) [10].
- 3) If SCT+ group,  $\geq 5$  items on the Barkley SCT Scale must be rated 3 ("often") or 4 ("very often") and total SCT symptom score  $\geq 26$ ; must have a T-score  $\geq 65$  on the Metacognition Index Subscale of the Behavior Rating Inventory of Executive Function - Adult Version (BRIEF-A) [11].
- 4) If SCT+ group, Impairment: must have a total score  $> 95$ th percentile on the Barkley Functional Impairment Rating Screen (Barkley Functional Impairment Scale (BFIS) [13].
- 5) If SCT- group,  $< 5$  items on the Barkley SCT Scale must be rated 3 ("often") or 4 ("very often") and total SCT symptom score  $< 26$ ; must have a T-score  $< 65$  on the Metacognition Index and Motivation Subscales of the BRIEF-A.

CONFIDENTIAL

## 4.2 Exclusion Criteria

- 1) Meets DSM-IV-TR criteria for a primary diagnosis of hyperactive-impulsive type ADHD as diagnosed via the ACDS v1.2.
- 2) Any other current psychiatric disorder, determined via the M.I.N.I , which requires pharmacotherapy treatment.
- 3) Current suicidal ideation or history of suicide attempts, based on the Columbia-Suicide Severity Rating Scale(C-SSRS) [15].
- 4) Lifetime history of bipolar disorder or any psychotic disorder as per the M.I.N.I
- 5) Pregnant, breastfeeding or women planning to become pregnant.
- 6) Positive urine drug toxicology are excluded.
- 7) Any other reason that, in the opinion of the investigator, prevents the subject from participating in the study or compromise the subject safety.

## 4.3 Subject Recruitment and Screening

We plan to recruit 120 adults (20% screen fail rate) to evaluate at the screening visit; approximately 100 adults with ADHD at two sites (NYU and Mount Sinai) to identify 50 SCT+ and 50 SCT-. We will accept referrals from other clinicians provided that the patients have given their clinicians permission to be contacted by the study team or the clinician has provided our contact information to the patient. We will advertise within and outside New York Langone Medical Center. There are flyers, radio and print advertisement created and approved for help with recruitment.

New York University Langone Medical Center and Mount Sinai will submit to their own IRBs. Subjects will be seen only at location consented. Mount Sinai will provide NYU with their IRB approvals for submission to the NYU IRB. Both locations will have their own staff and pharmacy.

Patients will be evaluated with clinical measures of SCT (Barkley SCT Scale), ADHD (ADHD-RS with prompts), executive function (BRIEF- A), assessment of other psychiatric disorders (M.I.N.I) global impairment (CGI), functional impairment (BFIRS), suicidality (C-SSRS), and neuropsychological function (neuropsychological battery). Only patients in the SCT+ cohort will enter the treatment phase of the protocol.

CONFIDENTIAL

Intended age for this study will require participants to be within 18 years to 60 years of age. There is no restriction as to gender, race or ethnic origin of patients.

We will contact patients from clinician referrals who have provided permission to be contacted or patients will call us from either a clinician referral or advertisement. They will be asked to provide verbal consent to see if they would be a possible candidate by completing a pre-screening questionnaire over the phone. After the pre-screen, a 5 minute general questionnaire about their mental or physical health, they will be asked to come in to the clinic at [name] for screening. An application for waiver of documentation of consent will be submitted as consent is obtained over the telephone and the questionnaire is minimal risk. All collected PHI from anyone who does not pass the pre-screening questionnaire or who decides not to participate will be immediately withdrawn.

At the study site, research staff will have patients read the consent form and opt to discuss with their private doctor and family. When the patient is ready, research staff will read and review each page of consent form. The research staff will ask if the patient understands and allow the patient to ask questions. After the patient has completed the inform consent process and has given consent by signing the consent document screening will begin. The patient is given a copy of the signed consent form. The original consent form will be filed in the patient's source documentation for the study. The research staff will document the inform consent process and file this with the patient's source documents.

If the patient does not agree to participate in the study the inform consent will be maintained; marked across the signature "declined" with a note to file regarding circumstances of patient's decline. See Consent Process Attachment [7]

#### **4.4 Early Withdrawal of Subjects**

Patients can withdraw or take back their permission to use and share his/her health information at any time. When the patient withdraws their permission, they will not be able to take back information that has already been used or shared with others.

Patients will be made aware and instructed on how to withdraw their permission by

CONFIDENTIAL

sending a written notice to the principal investigator for the study noted on page one of their consent form. If patient withdraws their permission, he/she will not be able to stay in this study. Patients will be withdrawn if, in the opinion of the study doctor, is no longer safe for the patient to participate in the study. We can get verbal permission to follow-up the patient in the event they suffer adverse events. We will document three attempts to contact the patient via phone. If unable to contact will send the patient a certified letter. Attachment [4]

#### **4.4.1 Data Collection and Follow-up for Withdrawn Subjects**

Subjects will be followed up after withdrawal for any adverse events and concomitant medications used since last in the research clinic. There will be three documented attempts to contact the patient. In addition we will send a certified letter explaining important to contact us for a follow-up appointment. These contact methods along with any information if obtained will be added to source documentation. See attached letter (Attachment 3)

## **5 Study Drug**

### **5.1 Description**

Vyvanse (Lisdexamfetamine Dimesylate) is manufactured by Shire. Vyvanse is a DEA class two, sympathomimetic amine. Its indications are for treatment of attention-deficit hyperactivity disorder. The initial adult dosage is 30mg with allowed adjustments in increments of 10mg or 20mg at weekly intervals. The maximum dosage is 70mg/day. Vyvanse is supplied in 20mg, 30mg, 40mg, 50mg, 60mg, and 70mg capsules. Contradictions with Vyvanse are use with an MAOI or use within 14 days of the last MAOI dosage. Vyvanse (Lisdexamfetamine Dimesylate) is a Category C and is not for use in nursing. [26]

### **5.2 Treatment Regimen**

Medication will not be dispensed until week 1 of the study. Then for four weeks the dose of LDX or Placebo will be dispensed starting at 30mg up to 70 mg per day with an intervening single-blind placebo washout period (2 weeks).

Block One: During the LDX/epoch, LDX/Placebo treatment will be initiated at a dose of 30mg/day at Visit 2 and can be titrated up (in the judgment of the investigator) in

CONFIDENTIAL

increments of 20mg, based upon clinical response and tolerability, to 50mg/day at Visit 3 and 70mg/day at Visit 4.

Subjects receiving daily doses of 50mg or 70mg of LDX/Placebo will be allowed to down titrate one dosage step of 20mg during Visits 3-5 if (in the judgment of the investigator) they are having issues in tolerability. The highest effective dose of LDX will then be maintained until Visit 6.

Placebo Washout: At this time the patient are in the washout placebo phase for two weeks.

Block Two: At the end of the Placebo Washout Phase, Visit 7 (week 6), participants will be initiated at a dose of 30mg/day and can be titrated up starting at Visit 8 (in the judgment of the investigator) in increments of 20mg, based upon clinical response and tolerability.

Subjects receiving daily doses of 50mg or 70mg of LDX/Placebo will be allowed to down titrate one dosage step of 20mg during Visits 8-10 if (in the judgment of the investigator) they are having issues in tolerability. The highest effective dose of LDX will then be maintained until Visit 11

### **5.3 Method for Assigning Subjects to Treatment Groups**

Due to the study being double blind, an unblinded research assistant will conduct the block randomization of the subjects under the supervision of the NYU pharmacy. The block randomization will choose patients to start either the Vyvanse or placebo phase for four weeks. After these four weeks there will be a two week washout, then again Vyvanse or placebo phase for another four weeks. At the end of the study, the patients will be asked safety questionnaires. The patient and the research staff will not know whether the patient is on Vyvanse or placebo. In case of an emergency, the pharmacy can break the blind with permission from the principal investigator. We will know if the patient is on Vyvanse or placebo after the blind is broken.

### **5.4 Preparation and Administration of Study Drug**

CONFIDENTIAL

This material is the property of the NYU School of Medicine and Langone Medical Center. Do not disclose or use except as authorized in writing by the study sponsor

When a patient is consented and prior to enrollment, the research staff will send the investigational pharmacy a copy of the informed consent. On the day of randomization, the research staff will inform the investigational pharmacy of patient status via secure e-mail. The investigational pharmacy will conduct the block randomization as noted in section 5.4. The study doctor will write a prescription for the patient noting that the study drug name is listed as Vyvanse/Placebo. The investigational pharmacist will prepare the study medication for patient dispensation, based on the block randomization and the prescription order. A patient specific label will be generated by the investigational pharmacy and affixed to the study drug bottle. The hard copy of the prescription will be provided to the investigational pharmacy to be filled and dispensed by the research pharmacist to the patient. The contact number of the NYU Investigational Drug Service (IDS) is [contact] and the general e-mail address is: [[contact]](mailto:[contact])

